#### **9.2.4 End-of-Study (EOS)**

All subject will have End-of-study visit before discontinued. If the EoS is equal to or less than 14 days from previous scheduled visit, the EoS visit can be omitted and the assessment will be the previous visit.

- Subject (if qualified) returns to office/CRU
- Vital signs
- Abbreviated Physical Exam
- ECOG status
- Laboratory Tests: hematology, chemistry & electrolytes, and urinalysis
- Assess AEs
- Assess Concomitant medication usage/confirmation
- Assess compliance by pill count
- Exploratory markers

#### **9.2.5 Unscheduled Visits**

The Investigator may at his/her discretion arrange for a subject to have an unscheduled assessment, especially in the case of adverse events (AEs) that require follow-up or an AE

Suzhou Kintor Pharmaceutical, Inc.  
Protocol#: GT0918-US-1002

Proxalutamide (GT0918)

considered by the Investigator to be possibly related to the use of study drug. The unscheduled visit page in the eCRF must be completed.

### **9.2.6 30-day safety follow-up “window”**

GT0918 is a new 2nd generation of androgen receptor antagonist. The phase I data shows that the average elimination half-life between 400 mg and 500 mg is approximately 7 days (189 to 267 hours). Thus the safety follow-up “window” is set for 30 days after last dose of study drug GT0918 for any possible drug-related AE or SAE. Drug-related AE should be followed up until complete resolution or equal to the level of baseline. The safety follow-up visit can also be done over the phone or in the office if there is SAE and clinically indicated. If subject starts with different treatment or therapy, the window of safety follow-up will be closed. Any AE and/or SAE unrelated to the study drug is not required to report.

- Safety assessment on the AEs.

## **10 EFFICACY ASSESSMENTS**

Efficacy measures, timing, and required tests are detailed in Section 14 (“Statistical Analysis”).

## **11 EXPLORATORY MARKERS**

- CTCs, ct-DNA and ct-RNA

## **12 SAFETY ASSESSMENTS**

Safety assessments (vital signs, physical examinations, electrocardiogram (ECG) recording, AEs, clinical laboratory results (routine hematology and chemistry) are to be performed at protocol-specified visits, as specified in the Schedule of Assessments.

### **12.1 Vital Signs**

Vital signs (body temperature, respiration rate, heart rate, systolic and diastolic blood pressure measurements) will be evaluated at the visits indicated in the Schedule of Assessments. All vital signs will be measured after the subject has been resting in a sitting position for at least 5 minutes. Blood pressure measurements are to be taken in the same non-dominant arm for the duration of the study. Body weight (without shoes) will be recorded whenever vital signs are recorded. Height (without shoes) and BSA will be recorded at screening only.

Suzhou Kintor Pharmaceutical, Inc.  
Protocol#: GT0918-US-1002

Proxalutamide (GT0918)

Vital sign measurements will be repeated manually if clinically significant or machine/equipment errors occur. Out-of-range blood pressure, respiratory rate or heart rate measurements will be repeated at the Investigator's discretion. Any confirmed, clinically significant vital sign measurements must be recorded as AEs.

## **12.2 Physical Examination**

Complete physical examinations (general appearance, skin, HEENT including thyroid, heart, lungs, abdomen, cervical and axillary lymph nodes, extremities, neurological, and musculoskeletal systems) will be performed at Screening (Day -21 to Day -1) and at continued treatment Cycles 2-24. In addition, medical history will be recorded at screening and prior to first dose at Cycle 1, Day 1; including smoking history, if applicable. 30 days after last dose, a physical exam will be performed.

An abbreviated physical examination to verify continued subject eligibility and to follow up any change in medical history will be performed at the visits indicated in the Schedule of Assessments. Symptom-driven limited physical examinations will be performed as clinically indicated at any study visit. All changes not present at baseline or described in the past medical history and identified as clinically noteworthy must be recorded as AEs.

## **12.3 Electrocardiogram**

A 12-lead resting ECG will be obtained at the visits indicated in the Schedule of Assessments. ECGs will be performed during Screening. At Screening, the Investigator will examine the ECG traces for signs of cardiac disease that could exclude the subject from the study. Additional ECGs will be done on Cycle 1 Day 1, Cycle 1 Day 29, Cycle 4 Day 1, Cycle 7 Day 1, Cycle 10 Day 1 Cycle 13 Day 1, Cycle 16 Day 1, Cycle 19 Day 1, Cycle 22 Day 1, Cycle 24 Day 28 and at the end of the study (or earlier if clinically indicated). An assessment of normal or abnormal will be recorded. If the ECG is considered abnormal, the abnormality will be documented on the eCRF. ECGs will be repeated if clinically significant abnormalities are observed or artifacts are present. ECGs will be archived for further evaluation as necessary. If technical issues impede the interpretation, all available ECGs at each time point will be used to interpret the result.

ECGs, including the heart rate, PR, QRS, and the QTc intervals will be calculated automatically by the ECG equipment and will be assessed by the investigator or their designee. The designated physician will review the ECGs to detect a prolongation of the QTc compared to the Baseline tracing. QTc intervals automatically determined by the ECG equipment will be acceptable for detection of prolongation, provided that it is confirmed by a qualified physician later. The mean of the QTc intervals collected at each time point will be compared to the Baseline tracing. For individual subjects, prolongation of the QTc will be defined as (a) an increase in the QTc to > 500 ms for a subject without pre-existing bundle-branch block; (b) an increase in the QTc to >

Suzhou Kintor Pharmaceutical, Inc.  
Protocol#: GT0918-US-1002

Proxalutamide (GT0918)

550 ms for a subject with a pre-existing bundle-branch block; or (c) an increase in the QTc by > 60 ms at any single time point or by >30 ms at 2 successive time points. In any case of QT prolongation detected by the investigative site, the tracing will be promptly forwarded to the medical monitor for confirmation.

**If QT interval prolongation is confirmed**, the next dose of study medication will be held until normalization of the QT interval has been observed by 2 sets of triplicate ECGs taken with a minimum of 1 hour apart. A grade 3 QTc interval prolongation (QTc >500 ms on 2 consecutive ECGs) will be considered a DLT and reported to sponsor immediately. In the case of any dysrhythmias that are believed by the investigator to be drug-induced, they will be treated with appropriate measures such as magnesium administration, anti-arrhythmics, temporary pacing, etc., until the arrhythmia resolves.

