### 8.6.3 Dose modification and missing dose

Treatment modifications will be made based on specified safety criteria. Subjects may skip or discontinue treatment with GT0918 if they experience at least one adverse event, (noted below), following their dose of GT0918, and are considered by the Investigator to be **“possibly”**, **“probably”** or **“definitely”** related to study drug. Treatment modifications must be reported to the project team and discussed with the assigned medical monitor.

- 1) For any subjects experiencing grade 3 or 4 hematologic and/or biochemical toxicity, study drug will be temporarily interrupted until toxicity resolves to grade 1 or better
- 2) For any subjects experiencing grade 2 non-hematologic toxicity with significant impact on subject's daily active life, such as asthenic condition (including asthenia and fatigue), hepatotoxicity, mental impairment and anxiety, study drug will be temporarily interrupted until toxicity resolves to grade 1 or better
- 3) If the Investigator considers that continuing study drug is clinically beneficial for the subjects, the treatment and dose can be resumed. For some subjects if dose reduction is safe and clinically appropriate, a dose range of 25-50% dose reduction from original starting dose can be considered. The dose modification and schedule must be

Suzhou Kintor Pharmaceutical, Inc.  
Protocol#: GT0918-US-1002

Proxalutamide (GT0918)

discussed prior to implementation with the assigned medical monitor. Possible dose reductions are proposed as follow.

- i. For dose cohort of 400mg: starting dose can be 200mg or 300mg
- ii. For dose cohort of 500mg: starting dose can be 300mg or 400mg

**Dose restoration:** If any subjects on reduced dose for 2 cycles or more, the subject will have an option for the dose modification, for example, either to remain on the same dose or increase one dose level up or resume initial dose. The dose modification shall be considered based on investigator's clinical judgement for the best interest and care of subject and it must be discussed with medical monitor before implemented and document CRF timely and properly.

The subject may discontinue study drug for up to 5 consecutive days without being discontinued for noncompliance, which is at the investigator's discretion and is to be noted on the eCRF.

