10. ECGs will be performed in triplicate at Screening, on Cycle 1 Day 1 and Cycle 2 Day 1 (Day 29). Single ECGs are to be conducted on Day 85, 169, and quarterly (every 3 month) during additional cycles. For any subject with abnormal or questionable ECG, monthly monitoring ECG is required. If there is reading error, artifacts or suspicious readings, triplicate readings with at least 15 min between each reading are recommended. The final test result will take the average of 3 readouts.

Suzhou Kintor Pharmaceutical, Inc.  
Protocol#: GT0918-US-1002

Proxalutamide (GT0918)

11. Exploratory markers of circulating tumor cells, ct-DNA and ct-RNA will be assessed every 3 cycles and at EOS/ET.
12. Subjects are eligible for additional cycles in a 6-month Extension Study if they complete 6 cycles of treatment and have “no disease progression”. The same dose levels will be kept for the additional cycles. Subjects will be assessed by Investigator/Medical Monitor or/and Sponsor at the end every 6 cycles (end-of-6/12/18/24 cycles) to be determined if to proceed into the next 6 cycle treatments. Subjects are required to have office visits monthly (every 4 weeks +/- 3days) and all assessments marked with “X” will be performed every 4 weeks unless specified otherwise.
13. CT/MRI/bone scan, ECG, and exploratory markers will be assessed every 12 weeks. TSH/T3/T4 and PT/PTT/INR will be assessed every 12 weeks only in the first 6 cycles.
14. EoS is used for subjects on study drug GT0918. If EoS is equal to or less than 30 days from previous scheduled visit or to next planned visit, the EoS visit can be either omitted or combined.
15. Safety follow-up is recommended 30 days after last dose of study drug GT0918 or/and EoS whichever occurs later for any possibly delayed drug-related SAE. For drug-related AE/SAE should be followed up until complete resolution or equal to level of baseline.
16. In concomitant medication, specify if pain medications are taken or not. If so, list name, dosage, frequency, etc.

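### Section 12.3 makes QTc above 500 ms on two consecutive ECGs a DLT for everyone, but mandates no dose hold for it in some subjects with bundle-branch block

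*Combined protocol and SAP*

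**What the plan says.** Section 12.3 defines QTc prolongation for individual subjects in three limbs:

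- (a) without BBB, an increase to above 500 ms;
- (b) with pre-existing BBB, an increase to above 550 ms;
- (c) for anyone, "an increase in the QTc by > 60 ms at any single time point or by >30 ms at 2 successive time points".

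Suspected prolongation goes to the medical monitor. Once it is confirmed, "the next dose of study medication will be held until normalization of the QT interval has been observed". The next sentence sets a different test: "A grade 3 QTc interval prolongation (QTc >500 ms on 2 consecutive ECGs) will be considered a DLT and reported to sponsor immediately". That sentence has no BBB allowance, and the only consequences it states are the DLT label and immediate reporting.

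Exclusion 7 (section 7.2) bars a baseline QTc of 500 ms or more and a personal or family history of long QT syndrome. BBB is not a listed exclusion, and limb (b) shows that such subjects are expected.

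Section 8.6.3 has two mandatory interruption rules. One is for subjects "experiencing grade 3 or 4 hematologic and/or biochemical toxicity, study drug will be temporarily interrupted"; the other is for those "experiencing grade 2 non-hematologic toxicity with significant impact on" daily life.

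**The concern.** A sponsor that calls an event dose-limiting would be expected to stop dosing when it occurs. Here the label and the stop depend on different cut-offs. Without BBB both use 500 ms, so the label always brings the hold with it. With BBB the hold cut-off moves to 550 ms and the DLT cut-off does not. A BBB subject can therefore meet the DLT test and fail every limb of the hold test. Nothing in the protocol then requires the next daily dose to be withheld; it is left to discretion. What is at stake is a safety rule for a small subgroup, not the sample size or any efficacy analysis.

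**Working it through.** The plan gives no figure to reproduce. The check is to write both rules as conditions and find where they part.

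**Inputs**

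| Item | Value | Source |
|---|---|---|
| Baseline QTc, b | at most 499 ms (whole ms) | 7.2, exclusion 7 |
| DLT test | q1 > 500 and q2 > 500 on consecutive ECGs | 12.3 |
| Hold test with BBB, limb (b) | q > 550 | 12.3 |
| Hold test, limb (c), single | q − b > 60 | 12.3 |
| Hold test, limb (c), repeated | q − b > 30 at two successive time points | 12.3 |

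**Step 1. Subjects with BBB.** Take readings that rise by 30 ms or less, so that neither part of limb (c) can be met. Then q ≤ b + 30. Since b ≤ 499, q is at most 499 + 30 = 529, which is below 550, so limb (b) is not met either. The DLT test needs q ≥ 501. Both conditions can hold only if b + 30 ≥ 501, that is b ≥ 471. The affected baselines are 471 to 499 ms:

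- b = 471: only q = 501 qualifies;
- b = 480: q from 501 to 510;
- b = 499: q from 501 to 529.

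**Step 2. Example.** Baseline 480 ms, readings 508 and 506 ms.

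- DLT test: 508 > 500 and 506 > 500, so met.
- Limb (b): neither exceeds 550, so not met.
- Limb (c), single: 508 − 480 = 28 and 506 − 480 = 26, neither above 60, so not met.
- Limb (c), repeated: 28 and 26, neither above 30, so not met.

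The result is a DLT with no mandated hold, however long the readings persist at that level.

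**Step 3. Lower baselines with BBB.** From 441 to 470 ms the gap is transient. A reading above 500 ms is then a rise of at least 501 − 470 = 31 ms, so limb (c) applies if it persists at the next time point. Below 441 ms any such reading is a rise of at least 501 − 440 = 61 ms, and limb (c) applies at once.

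**Step 4. Subjects without BBB.** Limb (a) uses the same 500 ms as the DLT test, so any tracing above 500 ms already meets the hold definition. There is no gap at tracing level.

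**Step 5. Does section 8.6.3 close it?** An asymptomatic QTc finding is neither haematologic nor biochemical, so the grade 3 or 4 rule does not reach it. The grade 2 rule requires a marked effect on daily life, which an ECG finding without symptoms does not have. The rest of that section permits interruption but does not require it.

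**The case against.** **The two cut-offs may be deliberate.** The first paragraph of section 12.3 sets a subject-specific trigger for action, with an allowance for BBB; the DLT sentence attaches a grade and a reporting duty. On that view, no hold at 508 ms from a baseline of 480 ms is simply what limb (b) provides. This explains how the text could have arisen. It does not explain why an event named dose-limiting should carry no dosing consequence.

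**The DLT sentence may be a subset of confirmed prolongation.** The example subject then has neither a DLT nor a hold. But the sentence states its own numerical definition with no BBB exception, so the literal reading is the more natural one.

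**Existing handling softens the effect.** This stands. Reporting is immediate. Footnote 10 to the Schedule of Assessments (16.1) requires monthly ECGs after an abnormal or questionable tracing. Section 8.2 has safety reviewed every cycle and lets the medical monitor call a review at any time. Investigators examine the screening ECG for cardiac disease that could exclude the subject. Section 3.2.1 describes the nonclinical QT risk as low. These steps inform people and permit a hold; none requires one.

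**Two stronger readings are tempting and are not supported.** A reader might infer that sites cannot tell whether to hold. On both the literal and the subset reading the answer is the same: a hold is not mandated. Only if the name of the DLT event were itself taken to satisfy the hold condition would the answer change, and then the hold would already apply.

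A reader might also see a second defect in the reading basis, because "The mean of the QTc intervals collected at each time point will be compared to the Baseline tracing" while the DLT test counts individual ECGs. A triplicate of 504, 502 and 488 ms has a mean of 1494/3 = 498 ms, so the two can differ. On treatment this arises only at Cycle 2 Day 1 or on repeat ECGs, since later scheduled ECGs are single. Footnote 10 already points to an answer: "The final test result will take the average of 3 readouts".

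**Conclusion.** The inconsistency is real and minor. For BBB subjects with a baseline of 471 to 499 ms and rises of 30 ms or less to above 500 ms, section 12.3 read literally defines a DLT without a mandated interruption, and no other section supplies one.

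The number affected is small. The documents give no BBB frequency. If it were 1% to 10%, which is an assumption, 60 × 0.01 = 0.6 to 60 × 0.10 = 6 of the 60 planned subjects would have BBB. Only those with a baseline in this narrow band and two readings above 500 ms would be affected, possibly none. The width of the band describes where the rules part; it is not a measure of likelihood.

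A reader might infer that the dose recommendation is compromised. The documents do not support that: no decision rule uses a DLT count, and sections 13.7 and 13.8 provide for no interim analysis or data monitoring committee that would act on one.

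**What to change.** Add one sentence to the hold paragraph of section 12.3: any QTc event that meets the DLT criterion also triggers the dose hold, whether or not the subject has BBB.

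The cost is amendment wording. No scheduled ECG is added; a subject who is held would have the release ECGs that the section already requires. The downside is that a few BBB subjects may be held who would not be held now.

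If the sponsor's clinical team instead intends the BBB allowance to govern the DLT label too, the DLT sentence should use 550 ms for these subjects. Their readings of 501 to 550 ms would then no longer count as a DLT.

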#### 12.4 Laboratory Assessments

Laboratory assessment samples are to be obtained at designated visits as detailed in the Schedule of Assessments.

**Table 1: Laboratory Assessments**

Hematology	Serum chemistry	Urine analysis (dipstick)
------------	-----------------	---------------------------

Suzhou Kintor Pharmaceutical, Inc.  
Protocol#: GT0918-US-1002

Proxalutamide (GT0918)

Full and differential blood count	Albumin	Appearance
Hematocrit (Hct)	Alanine aminotransferase (ALT)	pH
Hemoglobin (Hgb)	Aspartate aminotransferase (AST)	Protein
Mean corpuscular hemoglobin (MCH)	Alkaline phosphatase (ALP)	Glucose
Mean corpuscular hemoglobin concentration (MCHC)	Blood Urea Nitrogen (BUN) or Urea	Ketone bodies
Mean corpuscular volume (MCV)	Carbon dioxide (CO 2 )	Indicators of blood and WBCs
Platelet count	Creatinine	Specific gravity
Red blood cell (RBC) count	Electrolytes (Na, K, Cl, Ca, P)	Urobilinogen
White blood cell (WBC) count with differential	Glucose	
	Lactate dehydrogenase (LDH)	
	Total bilirubin	
	Direct bilirubin	
	Total cholesterol	
	Triglycerides	
	Testosterone every 28 days	
	PSA every 28 days	
Coagulation		
PT/PTT/INR		

Blood samples will be analyzed at a local laboratory facility. Urine samples will be analyzed by dipstick, and a microscopic analysis will be performed if the results of dipstick indicate abnormalities to be further investigated by a local laboratory. All laboratory reports must be reviewed, signed, and dated by the Investigator. A legible copy of all reports must be filed with both the subject's source documents and medical record (source document) for that visit. Any laboratory test result considered by the Investigator to be clinically significant should be

considered an AE (clinically significant AEs include those that require an intervention). Clinically significant abnormal values occurring during the study will be followed until repeat test results return to normal, stabilize, or are no longer clinically significant.

## 12.5 Adverse Events

### 12.5.1 Adverse Event Description and Reporting

An adverse event (AE) is any symptom, physical sign, syndrome, or disease that either emerges or, if present at screening, worsens during the study, regardless of the suspected cause of the event. All medical and psychiatric conditions (except those related to the indication under study) present at screening and up until the first dose of study medication will be documented in the medical history eCRF. Worsening of these conditions and newly emerged symptoms, physical signs, syndromes, or diseases should be noted on the AE eCRF during the study.

Progressed disease (PD) and death caused by PD are not AE/SAE and should not be reported on the AE page of the eCRF.

Laboratory test results will be recorded on the laboratory results pages of the eCRF. Laboratory test value abnormalities, if not clinically significant, should not be reported on the AE page of the eCRF as AEs. Clinically significant laboratory abnormalities should be recorded as AEs. Conditions that result from a pre-planned surgical procedure arranged before the subject enrollment, are not considered AE or SAEs if the expected conditions were known before study inclusion. Such medical condition should be reported in the subject's medical history.

Additionally, anticipated AEs for this study population, listed below, must be reported by Investigators to the Medical Monitor but will not be expedited on an individual basis. Instead these AEs will be reviewed in aggregate every 3 months by the Sponsor. This aggregate review may result in an expedited safety report.

#### List of Anticipated AEs for this Study

diarrhea	loss of appetite	pain in extremities
dizziness	nausea	Arthralgia/myalgia
fatigue/lethargy	vomiting	back pain
headache	constipation	hot flush
hypercholesterolemia	hyperglycemia	hyperglyceridemia

Suzhou Kintor Pharmaceutical, Inc.  
Protocol#: GT0918-US-1002

Proxalutamide (GT0918)

peripheral edema	anemia	fever/chills/flu-like symptoms
blurred vision	dry eyes	taste changes/sensitivity to salt
gastro-esophageal reflux	increased CK levels	onychoschizia
Spinal cord compression	Elevated transaminase	Liver injury
Hepatic failure	Hepatic cirrhosis	

**List of adverse events (potential AR antagonist class effects and AEs reported from enzalutamide and abiraterone in clinical trials):**

**Enzalutamide:** seizures, posterior reversible encephalopathy syndrome (PRES), hypersensitivity, embryo-fetal toxicity, hypertension

**Abiraterone:** hypertension, hypokalemia, fluid retention (from increased mineralocorticoid levels), hepatotoxicity (post-marketing experience)

Subjects will be asked about and instructed to report AEs at each study visit. All drug-related AEs are to be followed until resolution or until a stable clinical endpoint is reached.

All AEs are to be documented on the eCRF with reference to date of onset, duration, frequency, severity, relationship to study drug, action taken with study drug, treatment of event (if any), and outcome. Furthermore, each AE is to be classified as being serious or non-serious. Changes in AEs and resolution dates are to be documented on the eCRF.

The purposes of this phase II trial is to study safety and tolerability of GT0918, the period of collection of AEs is from the time of first dose to the last dose of study drug or EoS visit. The 30-day safety follow up “window” is set to capture possibly drug-related AE and/or SAE. Regardless if subject has discontinued from study drug, any drug-related AE or SAE is required to follow until the event is resolved or stabilized at a level of baseline.

When subject starts with new therapy, the safety window of AE collection is closed simultaneously. All drug-unrelated or irrelevant AEs/SAEs such as disease progression and/or from new treatment should NOT be reported.

Specific guidelines for classifying AEs by intensity and relationship to study drug are given in **Table 2** and **Table 3**.

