### 3.2.2 Clinical Studies

In the Phase I/II trial of GT0918 US 1001, part 1 study of dose escalation, 40 subjects have been treated with GT0918 at seven dose levels: daily 50 mg (n = 3), 100 mg (n = 6), 200 mg (n=6), 300 mg (n=7), 400 mg (n=7), 500 mg (n=6), 600 mg (n=5). All subjects progressed on multiple lines of therapies including, but not limited to, bicalutamide, abiraterone, enzalutamide, docetaxel, cabazitaxel, radium 223, sipuleucel T and pembrolizumab. No DLT has been identified in the planned dose escalation cohorts thus MTD is not defined. GT0918 has been shown generally well tolerated and it has some CTCAE grade 1 and 2 AEs reported, such as fatigue, lethargy, nausea, loss of appetite, anemia, hypercholesterolemia, hyperglycemia, hyperglyceridemia, hot flush, constipation, etc. Three events of 2 grade 3 fatigue, 1 grade 3 anemia, and one event of grade 4 elevated creatine kinase (CK) were reported. Stable disease by imaging scans at 20 weeks by dose group were; 1/50 mg, 1/100mg, 3/400mg, 1/500mg. PSA decreases were also seen among subjects with increasing dosing for a period of time. This is the part II study to further evaluate the safety and tolerability of 2 dosages: 400 and 500 mg in selected subjects with mCRPC progressed on prior treatment either abiraterone or enzalutamide. Early phase 1 study performed in China included 19 subjects who were treated with GT0918 in various doses 50 mg, 100 mg, 200 mg, 300 mg and 400 mg over 3 months. Mild to moderated drug-related AEs were reported, such as hypercholesterolemia, hyperglycemia, hyperglyceridemia, peripheral edema, hot flash, fatigue, nausea, constipation.

Therefore three more clinical trials (China Phase 1 Bioavailability Study, GT0918-CN-1001, GT0918-CN-1002) regarding to GT0918 bioavailability in healthy subject and as a monotherapy drug in mCRPC subjects have finished in China and five on-going GT0918 clinical trials in mCRPC and breast cancer subjects. More information regarding to these trials can be found in investigator brochure.

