### 3.2.3 Anticipated Clinical Risks/Benefits

GT0918, a new investigational second generation of androgen receptor antagonist, has been orally administrated daily to over one hundred subjects with mCRPC or metastatic triple negative breast cancer (mTNBC) with androgen receptor (AR) positive. It has been shown that GT0918 was generally well-tolerated with some CTCAE grade 1 and 2 AEs, such as fatigue, lethargy, nausea, loss of appetite, anemia, hypercholesterolemia, hyperglycemia, hyperglyceridemia, hot flush, constipation, hepatotoxicity etc. Two events of grade 3 fatigue and one event of grade 4 elevated creatine kinase (CK) were reported. All the participating subjects who had progressed disease after the prior standard and experimental therapies, including abiraterone and enzalutamide, showed promising clinical responses and disease control rate with the study drug GT0918. The ratio of risks versus benefits supports further clinical evaluations of

Suzhou Kintor Pharmaceutical, Inc.  
Protocol#: GT0918-US-1002

Proxalutamide (GT0918)

selected 2 doses of 400 mg and 500 mg in mCRPC and mHSPC subjects whose disease progressed after abiraterone or enzalutamide.

For hepatotoxicity of GT0918 monotherapy in mCRPC subjects, increased ALT and increased AST are the most common AEs in both China and the US. The severity is mostly grade 1-2. Among 2.0% (19/958) of the subjects reported grade 3 and 4 hepatotoxicity AEs that believed to be study drug related. 9 subjects developed drug induced liver injury and 2 subjects experienced hepatic failure (as of 11/18/2020).

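### Creatine kinase is not a scheduled test, so CK toxicity at 400 mg versus 500 mg would rest on investigator-prompted tests and could not be compared reliably

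*Combined protocol and SAP*

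**What the plan says.** Section 3.2.2 states that in the US dose-escalation study "40 subjects have been treated with GT0918 at seven dose levels", and that "one event of grade 4 elevated creatine kinase (CK) were reported". It is the only grade 4 event named there. Section 3.2.3 repeats the finding: "Two events of grade 3 fatigue and one event of grade 4 elevated creatine kinase (CK) were reported". In section 12.5.1 the list of anticipated adverse events includes "increased CK levels". The same section requires anticipated events to be reported to the Medical Monitor and reviewed in aggregate every 3 months.

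For measurement, section 12.4 says "Laboratory assessment samples are to be obtained at designated visits as detailed in the Schedule of Assessments". Table 1 has 16 serum chemistry entries, from albumin to PSA. LDH is one of them; CK is not. The visit lists in section 9.2 and the Schedule of Assessments with its footnotes do not add it.

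The primary endpoint (section 5.1) is selection of the recommended dose on safety, tolerability and dose exposure. Section 5.2 sets laboratory safety at 400 mg against 500 mg. Section 13.6 summarises laboratory results by dose level and time point. Section 8.6.3 has a rule that depends on biochemistry results: for "grade 3 or 4 hematologic and/or biochemical toxicity, study drug will be temporarily interrupted until toxicity resolves to grade 1 or better".

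**The concern.** The sponsor has seen a grade 4 rise in this analyte and expects more rises, but does not plan to measure it. The trial is open-label and uses local laboratories, so whether a subject's CK is ever measured depends on the judgement of staff who know the dose. A reported CK rate would then mix how often CK rises with how often someone looks.

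Two things are at stake. One is the safety profile by dose, which drives the dose recommendation: a table with few or no CK events could be read as reassurance when it reflects few tests. The other is subject safety: a grade 3 or 4 rise without symptoms could go unseen, and the existing section 8.6.3 rule would then have no result to act on.

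**Working it through.** **1. Is CK scheduled anywhere?** I set the anticipated events that are named as analyte changes against the Table 1 tests.

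| Anticipated event | Test in Table 1 |
|---|---|
| Hypercholesterolemia | Total cholesterol |
| Hyperglycemia | Glucose |
| Hyperglyceridemia | Triglycerides |
| Anemia | Hemoglobin |
| Elevated transaminase | ALT, AST |
| Increased CK | None |

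Five of six have a test; CK is the only one without. Table 1 is not a complete list of every test named (Schedule footnote 13 mentions TSH/T3/T4), but CK is in neither place. No reason for the omission is given.

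**2. Size of the Phase I signal.** The protocol gives no rate, so there is no stated figure to reproduce.
- Dose-level counts: 3 + 6 + 6 + 7 + 7 + 6 + 5 = 40.
- Rate: 1/40 = 2.5%.
- Exact (Clopper-Pearson) 95% interval: 0.06% to 13.2%.

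**3. Chance that at least one grade 4 event occurs,** 1 − (1 − p)^n:
- p = 2.5%, n = 30: 1 − 0.975^30 = 53%.
- p = 2.5%, n = 60: 1 − 0.975^60 = 78%.
- n = 30 at the interval limits: 1.9% (p = 0.063%) and 98.5% (p = 13.16%).

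These are chances that an event happens, not that it is missed.

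**4. Effect of prompted testing.** Suppose unscheduled tests find a fraction s of true cases. The documents do not give s, so the values below are assumptions. The chance of seeing at least one case in 30 is 1 − (1 − ps)^30.

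| s | p = 2.5%: expected cases; chance of ≥1 | p = 10%: expected cases; chance of ≥1 |
|---|---|---|
| 100% | 0.75; 53% | 3.0; 96% |
| 50% | 0.38; 31% | 1.5; 79% |
| 25% | 0.19; 17% | 0.75; 53% |
| 10% | 0.08; 7% | 0.3; 26% |

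**5. What zero events would mean.** If all 30 subjects in an arm are tested and none has an event, the one-sided 95% upper bound is 1 − 0.05^(1/30) = 9.5%. If only reported cases are counted, the number tested is unknown and no bound can be computed.

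**6. What scheduled testing would allow.** Power of Fisher's exact test with 30 per arm, full ascertainment and an assumed two-sided 0.05 level (the protocol sets none):

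| True rates | Power |
|---|---|
| 2.5% vs 10% | 4% |
| 5% vs 20% | 24% |
| 2.5% vs 20% | 37% |
| 2.5% vs 30% | 78% |

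Scheduled CK therefore gives sound descriptive rates, not a useful formal test, unless the difference is very large.

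**The case against.** A reader might infer that the trial cannot compare CK toxicity at all, or that the section 8.6.3 rule can never be triggered by CK. The documents do not support either. Section 9.2.5 lets the investigator arrange an unscheduled assessment. Sections 12.4 and 12.5.1 make a clinically significant laboratory result an adverse event. Section 13.6 tabulates adverse events by dose level, severity and relationship. The section 8.6.3 rule is not confined to Table 1 analytes. Myalgia is also on the anticipated list and subjects are asked about events at each visit, so a symptomatic rise has a route into the data. The gap is incomplete ascertainment.

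Nor are the 53% and 78% a measure of what would be lost. They rest on one case pooled over seven doses from 50 to 600 mg. Section 3.2.3 reports one grade 4 CK event in a paragraph about more than one hundred subjects. If that is the denominator, which the text does not make clear, the rate is below 1% and the chances fall below about 26% in 30 subjects (1 − 0.99^30) and 45% in 60 (1 − 0.99^60).

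It can also be said that the anticipated list governs reporting and is not a menu of tests: blurred vision and dry eyes are on it with no dedicated test. That is fair, so this is a gap rather than a contradiction. But those are complaints a subject can report. A CK rise is a laboratory value, and it is the only one on the list left untested.

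Finally, randomisation means that site differences in testing do not by themselves favour one dose. That stands. It does not remove the possibility that knowledge of the dose influences who is tested, and it does not correct an under-count common to both arms.

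**Conclusion.** The point holds as one of ascertainment. CK is not scheduled, so CK findings by dose would have no baseline, no tested denominator and no grade shifts. Rates at 400 mg and 500 mg would probably be under-counted and could not be compared reliably. Asymptomatic grade 3 or 4 rises could go unseen.

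The size of the loss cannot be stated, because the documents do not give the share of rises that prompted testing would miss. The occurrence figures show scale only: they assume that the pooled 1/40 applies to these doses, and the interval is too wide to say more than that an event is plausible. The clearest loss is the 9.5% bound that a clean result in 30 tested subjects would give. This is a cheap improvement to a descriptive safety trial, not a flaw that undermines it.

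**What to change.** Add CK to the serum chemistry column of Table 1 and to the Schedule of Assessments, at baseline and at the chemistry draws already planned. In section 13.6, summarise CK values, changes from baseline and grade shifts by dose, with the number tested at each time point. If the omission is deliberate, state the reason and say that CK event rates come from prompted testing only.

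The cost is one more local-laboratory analyte on blood already drawn, plus some incidental CK rises unrelated to the drug that will need adjudication. The comparison stays descriptive at 30 per arm. No dose or interruption rule changes.
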